The Frederick W. Thompson Anxiety Disorders Centre has experienced significant demand for services related to the treatment of Obsessive Compulsive Disorder (OCD), resulting in a significant wait time for service. Although Cognitive Behavior Therapy (CBT) is the most efficacious treatment intervention for OCD (McKay et al., 2015), there is a growing literature indicating the mindfulness based approaches can be beneficial in terms of managing acute mood and anxiety symptoms as well as reducing relapse risk following treatment (e.g., Huijbers et al., 2016). The National Institute for Health and Care Excellence (NICE) guidelines provide a framework for health professionals who provide integrated, comprehensive treatments for the management of mood and anxiety disorders. These guidelines suggest that clinicians provide clients with accessible, low intensity, low risk interventions as they await treatment. It may be that having clients engage in low intensity interventions while they wait for CBT treatment can prevent symptom exacerbation and improve their motivation to engage in subsequent hospital based treatments. Although past research has demonstrated the benefits of engaging in guided mindfulness meditation practice in terms of psychological symptom improvement, it is unclear whether self-guided meditation practice incorporating biofeedback could promote symptom alleviation for individuals experiencing OCD. The goal of this study is to examine the potential benefits of using a consumer grade EEG-based biofeedback device that allows clients to engage in home based mindfulness meditation practices while they are waiting to receive clinical services. Specifically, this study will investigate the effects of meditation home practice on symptom alleviation, as related to specific OCD related cognitive processes. Patients who are waiting to receive clinical services will engage in an initial clinical assessment prior to being offered service, which is standard clinical practice. Following a clinical assessment, the patient will be offered the opportunity to participate in the current study - regardless of their decision to participate, they will still receive treatment recommendations and be considered for an upcoming clinical treatment service as usual, as determined by the assessor. If they choose to be involved in this study, they will be randomized to one of two groups: either an eight week waitlist control condition, or an eight week mindfulness treatment condition. Participants in the mindfulness condition will receive a commercially available wireless EEG headset and a software package that provides guided meditation practices with auditory feedback. Participants will attend three sessions during the eight week protocol – each session involves completing a self-report questionnaire package (evaluating OCD symptoms, mindfulness and thought control strategies) and they will complete a brief open monitoring meditation practice using the Muse EEG headset. Participants in the meditation condition will engage in regular mindfulness practice during each week, and complete a brief online survey regarding their experience during the mindfulness practice, once per week.

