The study will be a randomized trial where subjects (N=100 Total, N=50 assigned to Group 1 (Mindfulness condition) or Group 2 (Control condition) will be randomly assigned to receive either 1) an eight week meditation program involving use of an EEG-based biofeedback device, or 2) wait list as per usual. The experimental design is a 2 (treatment condition) by 3 (assessment phase: baseline (week 0), mid treatment (week 4), and post-treatment (week 8)) repeated measures factorial design. Randomization will be completed

by staff separate from the research team using numerical randomization for consecutive referrals.

Data Analyses

A repeated measures multivariate analysis of variance (MANOVA) will be conducted with the two groups (guided mindfulness meditation or control wait list group) as the between-group variable and OCD symptom scores as the dependent variables. A mediation analysis will examine whether obsessive beliefs, engagement in thought control strategies, psychological flexibility, and mind wandering mediates treatment related changes in OCD symptom scores (YBOCS, OCI). A Latent Difference Score (LDS) analysis will examine longitudinal temporal relationships between OCD symptoms and each of the above mentioned variables. Daily practice data from the EEG headsets will be automatically uploaded to an encrypted server. These data will be made anonymous from the start of the study; subjects will be identified using their subject I.D. EEG data will be measured in latency windows selected according to prior research and determined from visual inspection of the waveforms. Analyses of variance (ANOVAs) will be computed on peak and mean amplitude using group as a between-subjects factor and session (pre or post), task condition, and electrode as within-subject factors.

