5.6 Benefits

The benefit of participating in this study involves the likelihood of improving significantly in both symptom measures as well as measures demonstrated to underlie treatment response in OCD.

6 Intervention:

MUSE Guided Meditation Practices: The guided meditation intervention will be administered using

Interaxxon's Muse device. Muse is a wireless EEG headset with an accompanying mobile device software application. The headset has 4 dry sensors (2 mastoid and 2 forehead sensors) and fits over the ears and extends at an angle over the middle of the forehead when properly fitted. Data are sampled at 220 Hz and referenced to Fpz channel. The data is communicated wirelessly to the mobile device application.

Participants are asked to engage in a daily mindfulness practice, with each practice lasting for a minimum of 20 minutes, once per day. Participants may engage in additional practices if they feel motivated to do so. To provide high-fidelity neurofeedback during meditation practice, Interaxxon has established an algorithm that involves a combination of frequency bands that have been associated with meditative states (Kerr, Sacchet, Lazar, Moore, & Jones, 2013). When the application determines that the participant's "mind wandered", biofeedback is provided in order to assist the participant with refocussing their attention on their meditation practice. The software application provides a guided pre-session calibration to customize neurofeedback to match participant experience prior to each training session. Calibration involves two brief exercises: in the first exercise, participants are asked to perform a word association task to simulate a period of mind-wandering. In the second exercise, participants are asked to relax and clear their minds as a brief induction of a focused attention state. These two calibration conditions are then entered into a machine learning algorithm to generate a session-specific signature of concentration and distraction customized to the participant. Calibration lasted 1 minute. Following calibration, guided meditation instructions were delivered through the paired smartphone/iPad, directing participants attention towards sensations of the breath, body, and/or cognition. Neurofeedback is delivered through auditory cues of wind and storm sounds, which increase in intensity with greater estimated distraction, and subsided towards calm with greater estimated stability of attention.

7 Costs and Payments

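### EEG arms are tested on peak as well as mean amplitude; peak rises with recording noise, so if signal quality came to differ between arms the peak ANOVA could show a spurious EEG effect

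*Combined protocol and SAP*

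**What the plan says.** Data Analyses in section 3.1 plans inferential ANOVAs on two EEG measures: "Analyses of variance (ANOVAs) will be computed on peak and mean amplitude using group as a between-subjects factor", with "session (pre or post), task condition, and electrode as within-subject factors". It does not name the term of interest (group main effect or group × session), and it ranks neither amplitude measure above the other. On the window it says: "EEG data will be measured in latency windows selected according to prior research and determined from visual inspection of the waveforms". It gives no window limits.

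Section 6 (Intervention) describes the device: "The headset has 4 dry sensors (2 mastoid and 2 forehead sensors", and "Data are sampled at 220 Hz and referenced to Fpz channel". The opening summary has participants attend three sessions at which "they will complete a brief open monitoring meditation practice using the Muse EEG headset"; this is not restricted to one arm. Home use is: "Participants in the mindfulness condition will receive a commercially available wireless EEG headset", and section 6 adds "Participants are asked to engage in a daily mindfulness practice", for at least 20 minutes.

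The documents state no artefact rejection, signal-quality criterion, minimum amount of usable data, noise matching between arms, or EEG exclusion rule.

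**The concern.** A window peak picks out the highest point of signal plus noise, so noise pushes it upward even when the brain signal is unchanged. Averaging over a window chosen independently of the noise has no such bias. This does no harm to the comparison while noise is equal between arms.

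The design gives a reason why noise might become unequal. One arm handles a dry-sensor headset daily for eight weeks; the other wears it only at study sessions. If practice improves sensor contact at the post session, noise falls in one arm only. Randomisation does not protect against this, because the change would be caused by allocation. The peak ANOVA could then report a group difference that reflects sensor contact. Better fit would lower peaks in the mindfulness arm, so the artefact would look like a reduction.

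**Working it through.** The plan gives no figure for the EEG analysis, so there is nothing to reproduce first.

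**Inputs from the documents.** Sampling rate 220 Hz (section 6); 50 per arm (section 3.1, Experimental Design); peak and mean amplitude, group, and pre/post session (section 3.1, Data Analyses).

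**Assumed, because not stated.** Window length, definition of peak (taken as the sample maximum), filtering, component size, noise level, between-person and session SDs, and alpha (two-sided 0.05).

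**Step 1: samples per window.** 220 × 0.100 s = 22; 220 × 0.200 s = 44.

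**Step 2: pure noise with SD s.** Write E[peak] = k·s; E[mean] = 0. From 40,000 draws of first-order autoregressive noise:

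| Autocorrelation | k, 22 samples | k, 44 samples | Peak drop if s falls 20% (22 samples): 0.2·k·s |
|---|---|---|---|
| 0 | 1.91 | 2.20 | 0.38 s |
| 0.8 | 1.48 | 1.85 | 0.30 s |
| 0.9 | 1.19 | 1.57 | 0.24 s |

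Simulated means were within 0.005 of zero.

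**Step 3: add a real signal.** With a 5 µV bell-shaped component (SD 50 ms) in the 100 ms window, the same 20% fall in noise lowers the peak by less. At noise SD 0.5–1 µV the drop is 0.14–0.18 s (autocorrelation 0.9) or 0.20–0.24 s (0.8). At 2 µV it is 0.22 s and 0.28 s. The range with signal present is therefore about 0.14–0.28 s, against 0.24–0.30 s with none.

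**Step 4: bias of the peak of a true 5 µV component, 200 ms window.**

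| Noise SD (µV) | 0.5 | 1 | 1.5 | 2 | 3 |
|---|---|---|---|---|---|
| White noise (µV) | +0.65 | +1.47 | +2.36 | +3.29 | +5.28 |
| 20 Hz low-pass noise (µV) | +0.24 | +0.72 | +1.31 | +1.95 | +3.40 |

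Mean amplitude: bias within 0.01 µV throughout. If noise falls from 1.5 to 1.0 µV in one arm, that arm's peak changes by 0.72 − 1.31 = −0.59 µV (low-pass) or 1.47 − 2.36 = −0.89 µV (white) with no change in signal.

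**Step 5: false-positive rates.** 50 per arm, no true effect, 1,500 replicates, between-person SD 2 µV, session SD 1 µV, 200 ms window. The interaction is a t-test on post minus pre; the group effect is a t-test on pre plus post. Entries are low-pass / white.

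| Noise SD | Peak, group × session | Peak, group |
|---|---|---|
| 1.5 µV in both arms | 3.9% / 4.3% | 5.7% / 5.6% |
| Stable gap: 1 vs 2 µV at both sessions | 4.8% / 4.7% | 87% / 99.5% |
| 1.5 to 1.25 µV, mindfulness arm only | 11% / 29% | 8% / 10% |
| 1.5 to 1.0 µV, mindfulness arm only | 34% / 76% | 11% / 22% |
| 2 to 1 µV, mindfulness arm only | 85% / 99.9% | 35% / 61% |

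Mean amplitude gave 3.8% to 6.3% for both terms in all scenarios. The simulation standard error near 5% is √(0.05 × 0.95 / 1500) = 0.56 points, so this is close to nominal.

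A stable gap cancels in the interaction but not in the group main effect. A gap that opens after baseline inflates both.

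**Step 6: the mean is protected only if the window is independent of the noise.** As an extreme case, a 100 ms window was placed, for each recording, where the mean was highest within 300 ms of pure noise. The expected mean was 0.61 s (autocorrelation 0.8) or 0.67 s (0.9). A 20% fall in noise then gives a spurious drop of 0.2 × 0.61 = 0.12 s to 0.2 × 0.67 = 0.13 s. Choosing windows on grand averages would give less.

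**The case against.** The strongest reply is that unequal noise is a supposition. Participants are recorded with the same headset in the same kind of session, and the documents do not say who fits it there. If staff do, most of any practice advantage disappears. This stands: a reader might infer that the arms will differ in signal quality, and the documents do not support that. They show unequal headset experience and no safeguard, and nothing more.

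Three other inferences also go too far.

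- That group × session is the tested term. Section 3.1 lists factors and names no term, so both routes in Step 5 remain open.
- That the planned mean-amplitude ANOVA already removes the problem. It does so only if windows are set independently of the noise, and the plan leaves them partly to inspection.
- That the zero-signal figures give the size. With a real component present the shift is smaller (Step 3).

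It can also be said that peak versus mean is secondary while the time-locking event, task condition and window limits are undefined, and that little hangs on the EEG analysis. It is absent from the hypotheses in section 2.2 and from the outcome measures listed in section 3.1, and it lies outside the symptom MANOVA, mediation and latent difference score analyses. That is fair, and it sets the severity. A disagreement between peak and mean would also be visible, but the plan does not say how it would be resolved.

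**Conclusion.** The point holds as a conditional, low-severity one. Testing peak amplitude exposes the EEG comparison to a bias that fixed-window mean amplitude avoids. If noise differs between arms, the peak ANOVA could show an effect with no brain change behind it: in the group main effect if the gap is stable, and in group × session as well if the gap changes after baseline. Under the assumed values, a noise fall confined to the mindfulness arm raised the peak group × session false-positive rate to between 11% (1.5 to 1.25 µV, low-pass) and 99.9% (2 to 1 µV, white).

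Those sizes rest on the assumed signal, noise, window and variance values. The direction of the bias with noise does not, provided peak means the maximum in the window. Whether noise will differ is not known. Symptom conclusions are unaffected.

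**What to change.** In Data Analyses, section 3.1:

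- Make mean amplitude the only inferential EEG measure.
- Fix the windows in advance from prior research, or choose them blind to group and session. Apply the same window to every recording, since even blinded selection for each recording lets noise back in (Step 6).
- Name group × session as the term tested.
- Report peak amplitude descriptively only, from equal amounts of artefact-free data per person and session, with the noise level shown by arm and session.

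The cost is a few sentences and one inferential ANOVA fewer, with no new data collection. The downside is that there is no inferential result for peak.

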3.2 Participant Information

Participant information will be stored electronically within the FWT Anxiety Disorder Centre. To ensure anonymity, all documents containing participant names and/or contact information will be stored separately from the data. The data will be kept separately from any identifying info, anonymized and giving a coded ID number for matching purposes only.

a) All electronic personal health information will be stored on an encrypted password protected USB key. All physical copies of the data will be stored in a secure area and access will be restricted to research investigators.

b) Participant information will be stored for a period of 10 years

3.3 Data Collection and Statistical Considerations

Clinical data will be collected and entered into a computerized database. Confidentiality of subjects will be protected by maintaining data in locked files in locked offices. Data are maintained in computer files that are accessible only to FWT Anxiety Disorders Centre staff. All data will be coded and subsequently stripped of personal identifiers. Information linking the codes with subject identifiers will be maintained in a secure manner separate from the data. Sunnybrook policy requires that research records be kept for a period of no less than 5 years.

4 Study Measures and Materials

Participants will complete pre, mid and post-intervention self-report measures assessing OCD symptom severity, OCD beliefs, the quality of their mindfulness practice, engagement in OCD thought control strategies, and whether participants experience spontaneous or deliberate "Mind Wandering" during their mindfulness practice. OCD symptom measures will include the self-report Yale-Brown Obsessive Compulsive Scale (YBOCS), and the Obsessive Compulsive Inventory-Revised (OCI-R). OCD beliefs will be measured by the Obsessive Beliefs Questionnaire (OBQ-44). The Five Factor Mindfulness Questionnaire (FFMQ) and the Mindfulness Practice Questionnaire (MPQ) will be used to measure the quality of participants' mindfulness practice. The Acceptance and Action Questionnaire (AAQ-II) will be used to measure psychological flexibility. The Thought Control Questionnaire (TCQ) will measure participants' tendency to engage in efforts to control intrusive thoughts. The Metacognitions Questionnaire (MCQ) will measure participants' beliefs about their thinking. The Mind Wandering Scale (MW) will be used to determine the extent to which participants experienced spontaneous or deliberate mind wandering during their mindfulness practice. Daily practice data

Version 2 Updated Friday, September 01, 2017

from the EEG headsets will be automatically uploaded to an encrypted server.

5 Human Subjects

5.1 Characteristics of subject population

Patients included for participation are those with a referral for FWT Anxiety Disorder Centre services.

5.2 Inclusion

All inclusion and exclusion criteria are consistent with the established guidelines for our service – there are no additional study specific criteria. Potential subjects are referred to the service with a query of OCD. Due to the nature of the assessment procedures, which include English-language self-report questionnaires and scales, the ability to communicate in written and spoken English is an inclusion criterion.

5.3 Exclusion

- a) those with active substance abuse/dependence
- b) suspected organic pathology
- c) recent suicide attempt/active suicidality
- d) active bipolar, psychotic disorder or post-traumatic stress disorder

5.4 Consent Procedures

The FWT Clinic secretary will call patients to book their psychological assessment appointments. At the end of the assessment appointment, participants will be introduced to the study at that time and they will be asked if they are interested in participating. Participants interested in hearing a detailed study explanation will be contacted by the study co-ordinator who will review the study details with the participant. For eligible and interested participants, a mail out package including applicable measures will be sent out along with the consent form. Participants will be asked to bring the consent form unsigned with them to the first information session. Written consent will be obtained in person by the study co-ordinator at that time who will address any questions or concerns before the first session.

5.5 Risks

There are no significant risks associated with the study. The only potential risk for participation is possible breach of confidentiality. However, the Frederick W. Thompson Anxiety Disorders Centre's staff will take extensive precautions to maintain the participants' confidentiality. Additionally, given that much of this information is already collected for clinical purposes, the risk to confidentiality should not be any greater than that of standard clinical care. There could also be a risk of some mild discomfort in answering some of the questionnaires. Again, this is not over and beyond the standard care and further, participants are explained that they may withdraw from the study at any time.

5.6 Benefits

The benefit of participating in this study involves the likelihood of improving significantly in both symptom measures as well as measures demonstrated to underlie treatment response in OCD.

6 Intervention:

MUSE Guided Meditation Practices: The guided meditation intervention will be administered using

Interaxxon's Muse device. Muse is a wireless EEG headset with an accompanying mobile device software application. The headset has 4 dry sensors (2 mastoid and 2 forehead sensors) and fits over the ears and extends at an angle over the middle of the forehead when properly fitted. Data are sampled at 220 Hz and referenced to Fpz channel. The data is communicated wirelessly to the mobile device application.

Participants are asked to engage in a daily mindfulness practice, with each practice lasting for a minimum of 20 minutes, once per day. Participants may engage in additional practices if they feel motivated to do so. To provide high-fidelity neurofeedback during meditation practice, Interaxxon has established an algorithm that involves a combination of frequency bands that have been associated with meditative states (Kerr, Sacchet, Lazar, Moore, & Jones, 2013). When the application determines that the participant's "mind wandered", biofeedback is provided in order to assist the participant with refocussing their attention on their meditation practice. The software application provides a guided pre-session calibration to customize neurofeedback to match participant experience prior to each training session. Calibration involves two brief exercises: in the first exercise, participants are asked to perform a word association task to simulate a period of mind-wandering. In the second exercise, participants are asked to relax and clear their minds as a brief induction of a focused attention state. These two calibration conditions are then entered into a machine learning algorithm to generate a session-specific signature of concentration and distraction customized to the participant. Calibration lasted 1 minute. Following calibration, guided meditation instructions were delivered through the paired smartphone/iPad, directing participants attention towards sensations of the breath, body, and/or cognition. Neurofeedback is delivered through auditory cues of wind and storm sounds, which increase in intensity with greater estimated distraction, and subsided towards calm with greater estimated stability of attention.

7 Costs and Payments

7.1 Research study payments

At the end of the study, participants will receive a stipend of \$40 for their involvement.

Thank you for completing the Y-BOCS checklist. Please make sure that you circled the 2 most upsetting obsessions that you currently experience, and the 2 compulsions that cause you the most difficulty. Please enter them here:

2 most upsetting obsessions (thoughts or images):

2 most upsetting compulsive behaviors:

Remember the definitions of obsessions and compulsions and the examples of each that you may have noted on the checklist. Please place a check mark by the appropriate number from 0-4 beside each question below. If you are not currently experiencing any obsessions or compulsions, you may simply enter zeros for those questions, then continue to the next question.

OBSESSIVE THOUGHTS: Review the obsessions you checked on the Y-BOCS Symptom Checklist to help you answer the first five questions. Please think about the last seven days (including today), and check one answer for each question.

1. **TIME OCCUPIED BY OBSESSIVE THOUGHTS:** How much of your time was occupied by obsessive thoughts? How frequently did these obsessive thoughts occur?

0 = None
1 = Less than 1 hour per day, or occasional intrusions (occur no more than 8 times a day)
2 = 1-3 hours per day, or frequent intrusions (most of the day are free of obsessions)
3 = More than 3 hours and up to 8 hours per day, or very frequent intrusions.
4 = More than 8 hours per day, or near-constant intrusions.

2. **INTERFERENCE DUE TO OBSESSIVE THOUGHTS:** How much did these thoughts interfere with your social or work functioning? Is there anything that you didn't do because of them?

0 = No interference	
1 = Mild, slight interference with social or occupational performance, but still perform	nance not impaired.
2 = Moderate, definite interference with social or occupational performance, but still r	nanageable.
3 = Severe interference, causes substantial impairment in social or occupational perfor	mance.
4 = Extreme, incapacitating interference.	
3. DISTRESS ASSOCIATED WITH OBSESSIVE THOUGHTS : How much distress obsessive thoughts cause you?	did your
0 = None	
1 = Mild, infrequent, and not too disturbing distress.	
2 = Moderate, frequent, and disturbing distress, but still manageable.	
3 = Severe, very frequent and very disturbing distress.	
4 = Extreme, near-constant, and disabling distress.	
4. RESISTANCE AGAINST OBSESSIONS: How much effort did you make to resist thought? How often did you try to disregard or turn your attention away from those the entered your mind?	
0 = I made an effort to always resist (or the obsessions are so minimal that there is no resist them).	need to actively
1 = I tried to resist most of the time (e.g., more than half of the time I tried to resist).	
2 = I made some effort to resist.	
3 = I allowed all obsessions to fill my mind without attempting to control them, but I control reluctance.	lid so with some
4 = I completely and willingly gave in to all obsessions.	

5. **DEGREE OF CONTROL OVER OBSESSIVE THOUGHTS:** How much control did you have over your obsessive thoughts? How successful were you in stopping or diverting your obsessive thinking?

_		

0 =Complete control

1 = Much control; usually I could stop or divert obsessions with some effort and concentration.

2 = Moderate control; sometimes I could stop or divert obsessions.

3 = Little control; I was rarely successful in stopping obsessions and could only divert attention with great difficulty.

4 = No control; I was rarely able to even momentarily ignore the obsessions.

OBSESSION SUBTOTAL (Add items 1-5

-5)		

COMPULSIONS: Review the compulsions you checked on the Y-BOCS Symptom Checklist to help you answer these five questions. Please think about the last seven days (including today), and check one answer for each question.

6. **TIME SPENT PERFORMING COMPULSIVE BEHAVIORS:** How much time did you spend performing compulsive behaviors? How frequently did you perform compulsions?

0 = None

1 = Less than 1 hour per day was spent performing compulsions, or occasional performance of compulsive behaviors (no more than 8 hours per day).

2 = 1-3 hour per day was spent performing compulsions, or frequent performance of compulsive behaviors (most hours were free of compulsions).

3 = More than 3 hours and up to 8 hours per day were spent performing compulsions, or very frequent performance of compulsive behaviors (during most hours of the day).

4 = More than 8 hours were spent performing compulsions, or near-constant performance of compulsive behaviors (hour rarely passes without several compulsions being performed).

7. **INTERFERENCE DUE TO COMPULSIVE BEHAVIOR:** How much did your compulsive behaviors interfere with your social or work functioning?

-			
Г			

- 0 = No interference.
- 1 = Mild, slight interference with social or occupational activities, but overall performance not impaired.
- 2 = Moderate, definite interference with social or occupational performance, but still manageable.

3 = Severe interference, substantial impairment in social or occupational performance.

4 = Extreme, incapacitation interference.

8. **DISTRESS ASSOCIATED WITH COMPULSIVE BEHAVIOR:** How would you have felt if you were prevented from performing your compulsion(s)? How anxious would you have become?

0 = Not at all anxious.

1 = Only slightly anxious if compulsions prevented.

2 = Anxiety would mount but remain manageable if compulsions prevented.

3 = Prominent and very disturbing increase in anxiety if compulsions interrupted.

4 = Extreme, incapacitating anxiety from any intervention aimed at reducing the compulsions.

9. RESISTANCE:	How much effort did you make to resist the compulsions? Or, how often did you try
to stop the compul-	sions?

0 = I made the effort to always resist (or the symptoms were so minimal that there was no need to actively resist them).

1 = I tried to resist most of the time.

2 = I made some effort to resist

3 = I yielded to almost all compulsions without attempting to control them, but I did so with some reluctance.

4 = I completely and willingly yielded to all compulsions.

Version 2 Updated Friday, September 01, 2017

10. **DEGREE OF CONTROL OVER COMPULSIVE BEHAVIOR:** How much control did you have over the compulsive behavior? How successful were you in stopping the ritual(s)?

0 = I had complete control.

1 = Usually I could stop compulsions or rituals with some effort and willpower.

2 = Sometimes I could stop compulsive behavior but only with difficulty.

3 = I could only delay the compulsive behavior, but eventually it had to be carried out to completion.

4 = I was rarely able to even momentarily delay performing the compulsive behavior.

COMPULSIVE SUBTOTAL (Add items 6-10)

Mindfulness Practice Questionnaire

This questionnaire is to be completed based on the mindfulness practices you completed during the past week

How many separate, planned mindfulness practices did you complete over the last seven days (last week)?

Describe the most important obsessive thought or image that you experience during these practices:

Describe the most important ritual that you resisted engaging in during these practices:

Т

Г

.

Section 1: Please rate each of the following statements using the scale provided. Write the number in the blank space beside each question that best describes your own opinion of what is generally true for you, considering all of the mindfulness practices you completed during the past week.

_

Т

_

	1 2 3 4 5		5							
	Never or very rarely true	Rarely true	Sometimes true	Often true	Very often or always true					
	fullery thuc				·					
1 I	noticed that when I	repeat the same mi	ndfulness practice,	the "peak" level of a	anxiety					
		1	xperienced decrease	1	2					
 	2. I was aware of physical sensations in my body and how thoughts and emotions are									
	onnected to my phy	-	,							
			ection between havi	ng obsessive thoug	hts and					
	ngaging in rituals.			0						
		ctices were complet	ed without engagin	g in rituals						
			ning, repeating, mer							
· · · ·	 		nation that I wasn't	,	f.					
	1 5			1 5						
6. I	learned that I need	to engage in rituals	or safety behaviour	s in order to experie	ence					
S	ymptom relief.		-	-						
7. I	was able to re-evalu	uate my appraisal (c	or interpretation) of	the obsessive thoug	ht or image					
	uring each mindful				-					
8. T	he mindfulness pra	ctices were complet	ed without engagin	g in safety behaviou	ırs					
(e.g., checking, reass	surance seeking, dis	traction, mental avo	oidance, using medi	cations).					
9. I	was not aware of di	istressing obsessive	thoughts or images	that I experienced of	during my					
	nindfulness practice									
10.	I learned something	g new – the outcome	e of my mindfulness	practices were wor	se than					
	what I had expected.									
		y attention to my ex	xperience in the pre-	sent moment, my ar	nxiety will					
	radually decrease.									
	•	l wandered, I was av	ware of how I felt al	bout this and how I	reacted to					
	his experience									
		to complete a forma	al, structured mindfo	ulness practice that	I decided on					
	n advance.									
			g the mindfulness pr	ractice may apply to	o my					
	veryday experience									
	•	ate an alternative un	derstanding of my i	nterpretation of the	obsessive					
tl	hought.									

Hawley, Rector & Richter (2015). Please do not use, copy or distribute without permission from one of the authors.

 OCI-R

The following statements refer to experiences that many people have in their everyday lives. Circle the number that best describes **HOW MUCH** that experience has **DISTRESSED** or **BOTHERED** you during the **PAST MONTH**. The numbers refer to the following labels:

0 Not at all	1	2 Madaratah i	3	F .	4 Extremely				
Not at all	A little	Moderately	A lot		cure	enne	зıу		
1. I have saved u	p so many things th	nat they get in the v	way		0	1	2	3	4
2. I check things r	more often than ne	cessary.			0	1	2	3	4
3. I get upset if ob	ojects are not arran	ged properly.			0	1	2	3	4
4. I feel compelle	d to count while I a	m doing things.			0	1	2	3	4
5. I find it difficult strangers or certa	to touch an object v ain people.	when I know it has	been touched by		0	1	2	3	4
6. I find it difficult	to control my own t	thoughts.			0	1	2	3	4
7. I collect things	I don't need.				0	1	2	3	4
8. I repeatedly ch	eck doors, window	s, drawers, etc.			0	1	2	3	4
9. I get upset if others change the way I have arranged things.						1	2	3	4
10. I feel I have to repeat certain numbers.						1	2	3	4
11. I sometimes have to wash or clean myself simply because I feel contaminated.						1	2	3	4
12. I am upset by will.	12. I am upset by unpleasant thoughts that come into my mind against my will.						2	3	4
13. I avoid throwing	ng things away bec	ause I am afraid I	might need them la	ater.	0	1	2	3	4
14. I repeatedly check gas and water taps and light switches after turning them off.						1	2	3	4
15. I need things to be arranged in a particular way.						1	2	3	4
16. I feel that ther	re are good and ba	d numbers.			0	1	2	3	4
17. I wash my ha	nds more often and	longer than neces	ssary.		0	1	2	3	4
18. I frequently ge	et nasty thoughts a	nd have difficulty in	n getting rid of them	า.	0	1	2	3	4

(OBQ-44)

This inventory lists different attitudes or beliefs that people sometimes hold. Read each statement carefully and decide how much you agree or disagree with it.

For each of the statements, choose the number matching the answer that *best describes how you think*. Because people are different, there are no right or wrong answers.

To decide whether a given statement is typical of your way of looking at things, simply keep in mind what you are like *most of the time*.

Use the following scale:

1	2	3	4	5	6	7
Disagree very much	Disagree moderately	Disagree a little	Neither agree or disagree	Agree a little	Agree moderately	Agree very much

In making your ratings, try to avoid using the middle point of the scale (4), but rather indicate whether you usually disagree or agree with the statements about your own beliefs and attitudes.

1.	I often think things around me are unsafe.	1	2	3	4	5	6	7
2.	If I'm not absolutely sure of something, I'm bound to make a mistake	1	2	3	4	5	6	7
3.	Things should be perfect according to my own standards.	1	2	3	4	5	6	7
4.	In order to be a worthwhile person, I must be perfect at everything I do.	1	2	3	4	5	6	7
5.	When I see any opportunity to do so, I must act to prevent bad things from happening.	1	2	3	4	5	6	7
6.	Even if harm is very unlikely, I should try to prevent it at any cost.	1	2	3	4	5	6	7
7.	For me, having bad urges is as bad as actually carrying them out.	1	2	3	4	5	6	7
8.	If I don't act when I foresee danger, then I am to blame for any consequences.	1	2	3	4	5	6	7
9.	If I can't do something perfectly, I shouldn't do it at all.	1	2	3	4	5	6	7

1	2	3					6		7		
Disagree very much	Disagree moderately	Disagree a little	Neither agree or disagree	Agree a	little		Agree lerately		Agree muc		
10. I must wo	ork to my full p	ootential at all	times.	1	2	3	4	5	6	7	
	tial for me to of a situation.		ossible	1	2	3	4	5	6	7	
12. Even min	or mistakes m	ean a job is n	ot complete.	1	2	3	4	5	6	7	
13. If I have aggressive thoughts or impulses about my loved ones, this means I may secretly want to hurt them.					2	3	4	5	6	7	
14. I must be	certain of my	decisions.		1	2	3	4	5	6	7	
15. In all kinds of daily situations, failing to prevent harm is just as bad as deliberately causing harm.					2	3	4	5	6	7	
16. Avoiding serious problems (for example, illness or accidents) requires constant effort on my part.					2	3	4	5	6	7	
17. For me, not preventing harm is as bad as causing harm.					2	3	4	5	6	7	
18. I should b	e upset if I ma	ake a mistake.		1	2	3	4	5	6	7	
	nake sure othe	-	•	1	2	3	4	5	6	7	
20. For me, th	hings are not ri	ight if they ar	e not perfect.	1	2	3	4	5	6	7	
21. Having na	asty thoughts r	neans I am a	terrible person.	1	2	3	4	5	6	7	
	t take extra pre rs to have or ca		•	1	2	3	4	5	6	7	
	o feel safe, I ha	1	-	1	2	3	4	5	6	7	
24. I should n	ot have bizarr	e or disgustin	g thoughts.	1	2	3	4	5	6	7	
25. For me, making a mistake is as bad as failing completely.			1	2	3	4	5	6	7		
26. It is essential for everything to be clear cut, even in minor matters.				1	2	3	4	5	6	7	
-	blasphemous t	-	sinful as	1	2	3	4	5	6	7	

1	2	3	4	5 Agree a			6		7	
Disagree very much							Agree derately		Agree muc	-
28. I should b thoughts.	be able to rid m	y mind of un	wanted	1	2	3	4	5	6	,
	e likely than ot m to myself or		accidentally	1	2	3	4	5	6	,
30. Having ba	1	2	3	4	5	6	,			
31. I must be	the best at thir	ngs that are in	nportant to me.	1	2	3	4	5	6	,
32. Having an really war	[1	2	3	4	5	6	,			
 If my actions could have even a small effect on a potential misfortune, I am responsible for the outcome. 					2	3	4	5	6	,
